Nasal high-frequency jet ventilation (nHFJV) following extubation in preterm infants

Short title: Nasal high-frequency jet ventilation (nHFJV)

Protocol version 1.7; 3/4/19

[name], [name]

Division of Neonatology

University of Utah School of Medicine

A. Abstract

This prospective, randomized trial involves extubating preterm infants from mechanical ventilation to nasal high-frequency jet ventilation (nHFJV) to assess whether this decreases the rates of reintubation compared to nasal intermittent positive pressure ventilation (NIPPV), which is currently a common practice. With this study, we aim to decrease the rates of reintubation and days requiring mechanical ventilation, which are both risk factors for bronchopulmonary dysplasia (BPD). Additionally, nHFJV may decrease rates of severe BPD, diagnosed at 36 weeks corrected gestation age (CGA).

B. Background

Premature infants often experience respiratory insufficiency requiring increasing respiratory support, including endotracheal intubation and mechanical ventilation. The need for invasive mechanical ventilation as well as the duration of intubation are risk factors for BPD (Dumka et al, 2011). Increasing efforts for early extubation to a non-invasive mode of support, such as continuous positive pressure ventilation (CPAP) or NIPPV, have been made. However, in these high risk preterm infants there remains a considerable rate of respiratory failure on CPAP requiring escalation in support, including reintubation (Barrington et al, 2001). Additionally, infants who have failed extubation experience higher rates of BPD and/or death (Manley et al, 2016; Chawla et al, 2017).

Use of non-invasive high frequency ventilation (HFV) has been described as a rescue method following failure of other non-invasive ventilator modes or as a means to increase the success post-extubation. When used as invasive high frequency ventilation, high frequency oscillatory ventilation (HFOV) or high frequency jet ventilation (HFJV) utilize supraphysiologic respiratory rates and small tidal volumes which has been shown to inflict less lung injury than conventional modes of ventilation (Cotton et al, 2001).

Using a mechanical newborn lung model, nasal HFV has improved CO₂ removal when compared to conventional NIPPV (Mukerji et al, 2013; Mukerji et al, 2015). Animal studies in the lab of [name] have shown improved ventilation and oxygenation in the high frequency nasal ventilation group versus the mechanical ventilation group in a preterm lamb model leading towards better alveolar formation noted histologically (Reyburn et al, 2008; Null et al, 2014).

Few small clinical studies have looked at the use of nasal HFV however many were for short periods of time. Preterm infants on CPAP showed a significant decrease in pCO₂ after being switched to nHFV for a two hour period (Colaizy et al, 2008). In a pilot trial investigating the use of nasal HFV immediately after extubation in high-risk preterm infants, it was noted that pCO₂ levels significantly decrease, although returned to pre-extubation values after discontinuing nasal HFV (Czernik et al, 2012). In a recent randomized controlled trial, 81 infants were randomized to nasal HFV or nasal CPAP following surfactant administration (Zhu et al, 2017). Infants in the nasal HFV group had a significantly decreased need for invasive mechanical ventilation compared to the nasal CPAP group, however their cohort had a mean gestation age of ~32 weeks (Zhu et al, 2017). None of these clinical studies noted any negative impact from using nasal HFV.

C. Significance and Purpose

Very low birth weight infants are at increased risk of requiring prolonged duration of mechanical ventilation and multiple intubations, both of which are risk factors for ventilator-induced lung injury and BPD. Thus, it is important to investigate respiratory support methods that are able to effectively oxygenate and ventilate these high risk preterm infants while reducing their risk of lung injury. Nasal high-frequency ventilation is one potential intervention that may decrease the risk of respiratory failure in very low birth weight infants. Small studies have shown effective respiratory support over short time periods in infants, however these studies use nasal high-

frequency oscillatory ventilation. To our knowledge there are no published studies looking at the use of nasal high-frequency jet ventilation in this high risk population.

D. Hypothesis and Specific Aims

We hypothesize that extubation of very preterm infants to nHFJV will significantly decrease the rates of reintubation compared to those infants extubated to NIPPV.

Our specific aims are:

1. To examine the rate of respiratory failure requiring reintubation and invasive mechanical ventilation (IMV) within 72 hours of initiating study intervention.
2. To examine the rate of respiratory failure requiring reintubation and IMV within 7 days of transitioning off of non-invasive study intervention
3. To compare the total number of days requiring intubation with mechanical ventilation
4. To compare the rates of moderate to severe BPD with and without altitude correction at 36 weeks CGA per criteria defined by 2001 NICHD Consensus Conference

E. Methods

1. **Trial design:** This is a prospective, randomized trial.
2. **Study site:** The study site will be the University of Utah Medical Center, a Level III neonatal intensive care unit with 52 beds.
3. **Population:** Infants born $24^{0/7}$ to $28^{6/7}$ weeks gestational age (GA) requiring invasive mechanical ventilation (IMV) and meet extubation criteria within the first 7 days of life
 - a. **Inclusion criteria:**

- i. $24^{0/7}$ to $28^{6/7}$ weeks GA
- ii. Intubated within 24 hours of life to synchronized intermittent mandatory ventilation (SIMV) or high frequency ventilation (HFV, includes HFOV or HFJV)
- iii. Meets unit guidelines for extubation within 7 days of life
 - 1. See Table 1 for outline of criteria
- iv. Infants intubated for surfactant replacement therapy via INSURE method (Intubation-Surfactant-Extubation) are eligible
- v. Initiation of treatment arm must occur within 6 hours of extubation
 - 1. If randomization occurs after the time of extubation, infants are eligible if FiO_2 requirements are $>30\%$
- vi. Consent obtained from parent/legal guardian

b. **Exclusion criteria:**

- i. Major congenital and/or chromosomal anomalies
- ii. Upper oropharyngeal anomalies

4. Randomization:

- a. Infants stratified by GA ($24^{0/7}$ – $25^{6/7}$ weeks, $26^{0/7}$ – $28^{6/7}$ weeks) and randomized in blocks of 4 to nHFJV or NIPPV group
- b. Randomization and initiation of treatment arm must occur within 6 hours of extubation
- c. Randomization will occur via sealed opaque envelopes

5. Intervention: Subjects will be randomized to be extubated to nasal HFJV (nHFJV) via the Bunnell Life Pulse high-frequency JET ventilator through a latex free PVC nasopharyngeal airway.

- a. Initial settings for nHFJV:
 - i. PEEP = 8
 - ii. HFJV PIP = 25
 - iii. On-time = 0.034 second
 - iv. Rate = 360 breaths per minute
 - v. Conventional rate = 10 breaths per minute
 - vi. I-time = 1 second
 - vii. Conventional PIP = 24
 - viii. FiO₂ adjusted to maintain target saturations per unit guidelines
- b. Available sizes of nasopharyngeal airway are 12 Fr and 14 Fr with an internal diameter of 3.0 mm and 3.5 mm, respectively, which will be attached to a 3.0 mm LifePort endotracheal tube adapter

6. Control group: Randomized subjects will be extubated to non-invasive positive pressure (NIPPV) via Hudson prongs.

- a. Initial settings
- b. PIP = 25
- c. PEEP = 6
- d. Ti = 0.6 sec
- e. Rate = 20 breaths per minute
- f. FiO₂ adjusted to maintain target saturations per unit guidelines
- g. Infants in the control group must remain on the Hudson prong interface for a minimum of 72 hours. At that time, can be transitioned to another interface to deliver NIPPV at the discretion of the medical team.

7. Data to be collected:

- a. **Specific Aim 1:** To examine the rate of respiratory failure requiring reintubation and IMV within 72 hours of initiating study intervention.
 - i. Reintubation criteria:
 - 1. Respiratory acidosis with pH <7.2 and PaCO₂ >60 mmHg on 2 successive blood gases on optimal ventilatory settings
 - 2. FiO₂ >0.6 to maintain SpO₂ >88% for >1 hour
 - 3. Impending respiratory failure noted by Silverman score >6
 - 1. Silverman, W. and Anderson, D.: *Pediatrics* 17:1, 1956.
 - 2. Depiction of scoring system noted in Figure 1.
 - 4. Severe/worsening apnea and bradycardia
 - 1. >3 episodes per hour requiring stimulation OR
 - 2. >1 episode of apnea requiring bag-mask ventilation in 24 hours
- b. **Specific Aim 2:** To examine the rate of respiratory failure requiring reintubation and IMV within 7 days of transitioning off of non-invasive study intervention.
- c. **Specific Aim 3:** To compare the total number of days of intubation with mechanical ventilation in the two study arms
- d. **Specific Aim 4:** To compare rates of moderate to severe BPD with and without altitude correction at 36 weeks CGA per criteria defined by 2001 NICHD Consensus Conference

8. Procedure/Protocol

- a. Identify infants meeting inclusion criteria within the first 24 hours of life

- i. If infant meets extubation criteria within the first 7 days of life, approach care provider for permission to obtain consent from parents/legal guardian
 1. Record patient and maternal demographic information.
- b. Ensure standard of care transcutaneous monitor (TCM) is placed prior to initiation of study intervention
 - i. Blood gases ordered per clinical practice
- c. Randomized infants extubated to nHFJV or NIPPV
 - i. Nasopharyngeal airway to be replaced in alternating nares every 48 hours to decrease risk of skin breakdown
- d. Respiratory settings adjusted to maintain target blood gas and/or TCM values
 - i. Goal: pH >7.2, PaCO₂ 45-60 mmHg, PaO₂ 60-80 mmHg
 - ii. Adjustment of nHFJV support as indicated in Table 2
 - iii. Adjustment of NIPPV support as indicated in Table 3
- e. Record vital signs (heart rate, respiratory rate, blood pressure) and ventilator support, including FiO₂, TCM/PaCO₂ and Silverman score for the first 24 hours of study support as follows: every 1 hour for three recordings then every 3 hours for three recordings and then every 6 hours for two recordings. Subsequently we will record this data every 12 hours until 48 hours and then every 24 hours for the remaining 7 days of the study period.
- f. Infant can be transitioned to CPAP via binasal prongs and/or mask when on minimal settings of the respiratory intervention for \geq 24 hours with acceptable oxygen saturations and TCM
 - i. Minimal nHFJV settings
 1. PEEP of 6, IMV rate of 0, HFJV PIP of 15, HFJV rate of 360 breaths per min, FiO₂ \leq 0.3

2. Transition to CPAP of 6 cm H₂O
 - ii. Minimal NIPPV settings
 1. PEEP of 5, PIP of 15, rate of 5 breaths per minute
 2. Transition to CPAP of 6 cm H₂O
 - iii. At the discretion of the attending physician, infant can be placed on bubble CPAP (bCPAP) or ventilator-interface CPAP.
- g. Criteria for termination of non-invasive study mode:
 - i. Respiratory failure meeting reintubation criteria as noted above
 - ii. At the request of the attending physician and/or parent/legal guardian
 - iii. Upon transfer of infant to Primary Children's Hospital for non-respiratory medical/surgical care
- h. Continue study respiratory intervention for 7 days, after which the respiratory support will be transitioned from nHFJV to another respiratory support modality of the attending physicians choosing.

9. Statistical Analysis: Data will be de-identified and analyzed on an intent to treat basis.

Statistical analysis will be performed using SPSS (version 25, IBM, Armonk, NY). The primary outcome and other categorical measures will be analyzed by Chi-square or Fisher's Exact test. Student's *t* test will be used for analysis of normally distributed continuous data and Mann-Whitney *U* test will be applied for ordinal data or continuous data that is not normally distributed. Two-sided P values of less than 0.05 will be considered to indicate statistical significance, and no adjustments will be made for multiple comparisons

10. Population and Recruitment Time:

- a. Approximately 60 infants born 24 0/7 to 28 6/7 weeks GA are born at the UUMC NICU each year
 - i. Estimated sample size is 40 infants (n=20 per group) This is a pilot study designed to test feasibility and safety of the nHFJV. However, the sample size proposed may allow identification of possible significant benefits. Based on historical failure rates in this patient population, including a recent study from Zhu et al, the estimated failure approaches 50% with the current standard. If we were able to show a reduction in that failure rate by 50% (from 50% to 25%, as shown in the Zhu, et al study) we would approach a P value of 0.05 by Chi-squared analysis.
 - 1. Zhu X-W, et al. Pediatric Pulmonology, 2017; 52(8)
- b. Expected time to complete study from initiation through closeout is approximately 2 years.

F. Risks and Benefits

NIPPV is a routine and well known mode of respiratory support with a few known risks, including air leaks, gaseous distension/discomfort and skin breakdown at the site of the prongs/mask. Effort is made to decrease the gaseous distension by allowing the enteric tube placed for enteral feeds to vent periodically throughout the day. We do not anticipate higher risk in the patients randomized to the nHFJV group. The nasopharyngeal airway will be replaced in alternating nares in the nHFJV group every 48 hours to decrease the risk of skin breakdown.

Potential benefits to study participants assigned to the nHFJV group may include decreased risk of reintubation and decreased days requiring mechanical ventilation. This improvement may translate to decreased severity of BPD at 36 weeks CGA. Benefits to society include increased

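### Aim 2 starts its 7-day reintubation clock at an undefined event and states no denominator, so on two of three possible readings reintubations on study mode after 72 hours are missed

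*Combined protocol and SAP*

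**What the plan says.** The hypothesis in section D is that nHFJV "will significantly decrease the rates of reintubation compared to those infants extubated to NIPPV". Two of the four aims are reintubation rates.

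- Aim 1 (sections D and E.7.a): "To examine the rate of respiratory failure requiring reintubation and invasive mechanical ventilation (IMV) within 72 hours of initiating study intervention".
- Aim 2 (section D, repeated in E.7.b): "To examine the rate of respiratory failure requiring reintubation and IMV within 7 days of transitioning off of non-invasive study intervention". E.7.b adds no definition, denominator or scoring rule.

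Section E.8 describes how an infant can leave the study mode, in three items:

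- E.8.f: *transitioned* to CPAP after at least 24 hours on minimal settings. This is permitted in both arms and depends on how the infant responds.
- E.8.g: *termination* of the study mode, on meeting the reintubation criteria, on request of the physician or family, or on transfer to another hospital.
- E.8.h: the study mode continues for 7 days, after which support is *transitioned*. This sentence names only nHFJV.

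Section E.9 says "Data will be de-identified and analyzed on an intent to treat basis" and "The primary outcome and other categorical measures will be analyzed by Chi-square" or Fisher's exact test, two-sided at 0.05. It makes no exception for Aim 2. Section E.10 plans 20 infants per group.

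**The concern.** Aim 1 has a fixed origin and a fixed length, so every infant who starts the intervention has a defined window. Aim 2 starts from something that happens after randomisation, that can depend on how well the assigned mode works, and that some infants may never reach. Two analysts could build different Aim 2 data sets from the same 40 infants, each following the text.

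Aim 2 is also the only reintubation rate that looks past 72 hours. If it leaves out infants whose study mode failed late, the reported rates do not fully answer a hypothesis about reintubation. Those failures would then show only indirectly, as ventilator days in Aim 3. The verb in Aim 2 is *examine* rather than *compare*, but Aim 1 uses the same verb, and section E.9 sends categorical measures in general to a significance test.

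**Working it through.** The plan gives no figure specific to Aim 2, so there is none to reproduce. The check is to set the sections side by side and follow one infant through them.

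**Inputs.** Aim 1 window: 72 hours from initiation (section D). Aim 2 window: 7 days from transitioning off (sections D and E.7.b). Planned study mode: 7 days (E.8.h). Arm size: 20 (E.10).

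**Test case (assumed).** An infant is still on the assigned mode at day 5, has not moved to CPAP, and is then reintubated. Day 5 is 5 × 24 = 120 hours. Since 120 > 72, this is not an Aim 1 event. By E.8.g the study mode ends by termination. Aim 2 can then be read in three ways.

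| Reading | Aim 2 denominator | How the day-5 infant is scored | What remains wrong |
|---|---|---|---|
| 1. Termination is not transition | Only infants who transitioned | Not in the analysis | Groups are not as randomised; event is in neither rate |
| 2. Intent to treat keeps everyone | All 20 per arm | Non-event, or unscored | Groups are as randomised; event is in neither rate |
| 3. Termination counts as transitioning off | All who leave the mode by any route | Event, at time zero | Follow-up from initiation is unequal |

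Reading 1 follows most naturally from the different words in E.8.f, E.8.g and E.8.h. Nothing in the text excludes the other two.

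**Unequal follow-up under reading 3.** The window closes 7 days after exit. With assumed exits at day 3 and day 7, follow-up from initiation ends at day 3 + 7 = 10 and day 7 + 7 = 14.

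**Control arm.** An nHFJV infant still on study mode at day 7 has a transition under E.8.h. For an infant still on NIPPV at day 7, no text says whether, or when, the Aim 2 clock starts.

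**Size.** Each infant missed under reading 1 or 2 is 1/20 = 5 percentage points of the randomised arm. The number of such infants cannot be derived from the documents.

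**Does a fixed origin raise a new problem?** Section E.4.b says "Randomization and initiation of treatment arm must occur within 6 hours of extubation". If both follow extubation, they differ by at most 6 hours. If *within* covers both sides of extubation, they differ by at most 12 hours. A 14-day window is 14 × 24 = 336 hours, so the difference is at most 6/336 = 1.8% or 12/336 = 3.6% of it. The choice between the two origins matters little.

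**The case against.** The strongest reply has four parts.

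*Intent to treat already supplies the denominator.* This is a fair reading. If it is adopted, the criticism that the arms are no longer those randomised falls away. It does not say how to score an infant reintubated on study mode after 72 hours, so the missing events remain.

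*Failure after the mode is withdrawn is a legitimate question.* It is. Section B cites a pilot in which pCO₂ fell on nasal HFV and went back to its pre-extubation level once that support stopped. Unequal time from initiation is inherent in any such endpoint, since each infant still has 7 days from exit. This supports keeping the result as a description, but not as the only reintubation rate after 72 hours.

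*Defining the event, the denominator and the status of each exit would be enough.* That would cure the ambiguity. If the definition chosen were reading 1 or 2, the late events would still be missed, so a definition alone is sufficient only if it counts them.

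*This is a 40-infant pilot.* That limits the consequence but does not remove it, because a between-arm test is planned.

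A reader might go further and infer that Aim 2 will certainly be restricted to infants who transitioned, or that it will favour one arm. The documents support neither: the restriction is one of three readings, and nothing in them gives the rate of late on-mode reintubation by arm.

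**Conclusion.** The concern holds as a defect of definition with a conditional consequence. It is certain that Aim 2 has no stated time zero, no denominator and no rule for infants who never transition. Under readings 1 and 2, the only reintubation rate after 72 hours misses on-mode events, at 5 percentage points of the arm per infant. Under reading 1 the test also does not compare the randomised groups. Under reading 3 no event is lost, and only follow-up from initiation differs.

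The size and direction of any bias are unknown. Two broader inferences should be resisted. The 72-hour comparison is not compromised: Aim 1 has its own fixed window. Late reintubations are not lost to the trial either, because they still add to the ventilator days in Aim 3. The point should be fixed, but it concerns one later-reintubation aim of a pilot.

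**What to change.** 1. Make the tested between-arm late comparison reintubation with IMV within a fixed window, for example 14 days (7 days of intervention plus 7), in all randomised infants by assigned arm. Count from initiation, or from randomisation if the intervention never starts. Score on-mode reintubations as events, and state the rule for death before reintubation.
2. Keep reintubation within 7 days of transition as a descriptive result among infants who transitioned, with their number given per arm. State which events start the clock and how each exit in E.8.g is classified.
3. Reconcile E.8.h, which names only nHFJV, with the control arm. No clinical rule is proposed here.
4. Leave Aim 1 unchanged.

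**Cost.** The wording of Aim 2 and section E.9 changes. The compared endpoint will contain the Aim 1 events and will no longer isolate failure after withdrawal, which the descriptive result retains. Reintubation dates are needed to day 14, including after transfer. The scheduled recordings in E.8.e end with the 7-day study period, so the dates must come from intubation records. That Aim 3's count of total days draws on such dated records is an assumption; the protocol does not say so.

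### A single fixed block size of 4 at one site with visibly different arms makes up to one third of allocations deducible before enrolment, an avoidable risk of selection bias

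*Combined protocol and SAP*

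**What the plan says.** Section E.4 sets out the randomization in three items. Item a starts "Infants stratified by GA", names two bands (24 to 25 weeks and 26 to 28 weeks), and has infants "randomized in blocks of 4 to nHFJV or NIPPV group". Item b requires randomization and the start of treatment within 6 hours of extubation. Item c says "Randomization will occur via sealed opaque envelopes". The section does not describe varying block sizes or sequential numbering of envelopes, and it does not say who makes the list or holds the envelopes.

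The single site is "a Level III neonatal intensive care unit with 52 beds" (E.2). The jet ventilation arm is delivered "through a latex free PVC nasopharyngeal airway" (E.5). For the control arm, "Randomized subjects will be extubated to non-invasive positive pressure (NIPPV) via Hudson prongs" (E.6). No masking is described anywhere.

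Before any infant is allocated, E.8.a.i has the study team "approach care provider for permission to obtain consent from parents/legal guardian". E.10.a.i plans 40 infants, 20 per group.

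**The concern.** Opaque envelopes stop anyone reading the next card. They do not stop someone working it out from the cards already opened. When every block has exactly four places, two per arm, the fourth allocation always follows from the first three, and the last two follow whenever the first two agree. Past allocations can be seen at the bedside because the interfaces differ, and with one site there are only two sequences to follow.

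Foreknowledge matters only if someone can act on it before allocation. E.8.a.i provides such a step, because a care provider can decline the approach to parents. If that decision came to depend on the expected arm, the two groups could differ in baseline risk. The chi-square or Fisher test planned in E.9 would neither detect nor remove the difference.

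**Working it through.** The plan gives no figure for predictability, so there is none to reproduce.

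**Inputs.** Block size 4 and two strata (E.4.a); 1:1 allocation and 40 infants (E.10.a.i).

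**Certain knowledge in one block of 4.** There are six equally likely sequences: AABB, ABAB, ABBA, BAAB, BABA, BBAA. An allocation is known when one arm is already used up in the block.
- Places 1 and 2: never known.
- Place 3: known in 2 of 6 sequences (AABB, BBAA), so 1/3.
- Place 4: always known, so 1.

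Expected share = (0 + 0 + 1/3 + 1)/4 = 33.3%. A single block gives 25% or 50%.

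**Over 40 infants.** Ten filled blocks give 40 × 1/3 = 13.3 known allocations (95% range about 11 to 16). Part-filled last blocks lower this. For example, strata of 6 and 34 hold 1 + 8 = 9 full blocks, with two infants left over in each stratum who cannot be known, so 9 × 4/3 = 12.0. Over all splits with 4 to 20 infants in the smaller stratum, the expected number is 12.0 to 13.3 of 40 (30.0% to 33.3%).

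**Best guess.** The observer guesses the arm with more places left and tosses a coin when they are equal.
- Place 1: 1/2.
- Place 2: 2/3.
- Place 3: (1/3 × 1) + (2/3 × 1/2) = 2/3.
- Place 4: 1.

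Average = (1/2 + 2/3 + 2/3 + 1)/4 = 17/24 = 70.8%.

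**Alternatives.** Fixed sizes come from the same enumeration. Varying sizes come from simulation with 12 to 28 infants per stratum. The simulated observer sees all past allocations and knows the possible sizes, but not the size of each block, and updates by Bayes' rule.

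| Scheme | Known with certainty | Best guess correct |
|---|---|---|
| Fixed 4 (as planned) | 33.3% | 70.8% |
| Fixed 6 | 25% | 68.3% |
| Fixed 8 | 20% | 66.6% |
| Random 2 or 4 | about 10% | about 72% |
| Random 4 or 6 | about 6% | about 68-69% |
| Random 2, 4 or 6 | about 4% | about 69-70% |

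With sizes 4 and 6, about 0.06 × 40 = 2.4 allocations would be certain, instead of 12.0 to 13.3. Best-guess accuracy above a coin toss goes only from 20.8 to about 18.5 points (at 20 infants per stratum).

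**Possible size of bias (assumption only).** The documents give no basis for how far steered infants would differ. If the whole known third were steered, and those sent to the two arms differed in failure risk by 10, 20 or 30 points, the arm difference would shift by one third of that: 3.3, 6.7 or 10 points. The difference considered in E.10.a.i is 50% − 25% = 25 points.

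**The case against.** The strongest reply is that one third is a ceiling. It applies to someone who knows the block size and keeps a complete, ordered tally for each gestational-age stratum. If recruitment filled most of the roughly 2 years in E.10.b (an assumption), enrolment would run at about 40/24 = 1.7 infants a month across two sequences in a 52-bed unit. Keeping such a tally is feasible, but it would not happen without effort. This stands, and the figure should be read as an upper bound.

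Second, a person minded to steer infants needs only a good guess, and varying the block sizes barely improves on 70.8%. This also stands. It is why changing the sizes alone is not enough, and why withholding them and separating list preparation from the clinical team belong in the fix.

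Third, E.10.a.i calls the trial a pilot for feasibility and safety. That lowers the stakes but does not remove them: section D states a comparative reintubation hypothesis, and E.9 tests it at a two-sided 0.05.

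A reader might go further and infer that every staff member knows the block size, that the care provider has seen the earlier allocations, or that this person chooses when to extubate. The documents say none of these things. They do not say who receives the protocol. E.8.a.i gives the care provider only permission over the approach to parents, and E.3.a.iii ties extubation to unit guidelines. A reader might also argue that one steered infant could carry the result across the significance threshold. Sensitivity to a single outcome comes with 20 infants per arm under any block scheme, so it does not measure this problem.

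**Conclusion.** The concern holds as a design weakness that is cheap to avoid. With blocks fixed at 4, up to one third of allocations (12.0 to 13.3 of 40) could be known with certainty before enrolment and about 71% guessed correctly, and the envelopes do not prevent it.

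The result rests on an observer who knows the block size and follows each stratum. That the trial is unmasked is inferred from the different interfaces and the absence of any masking text. The permission step in E.8.a.i is enough to give foreknowledge a route to influence who enters. The documents do not support reading this as evidence that allocations were predicted or enrolment steered, and any figure for the resulting bias depends on assumed risk differences.

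**What to change.** In E.4.a, replace the fixed size with *randomly permuted blocks of varying size within gestational-age stratum*. Keep the sizes out of the protocol, in a randomization document that enrolling and treating staff cannot see. State in E.4.c that the list and envelopes are prepared by someone already available outside the clinical team. Sizes 4 and 6 would serve. Sizes 2 and 4 would not, because best-guess accuracy does not improve. A larger fixed block still leaves 20% to 25% certain.

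The cost is a line or two of protocol wording and a new envelope list for the allocations that remain. The maximum end-of-list imbalance per stratum rises from 2 to 3 if the largest block is 6. No clinical procedure changes.
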